### **Primary Outcome Measurements:**

For the participants with chronic GI dysbiosis, the efficacy of FMT treatment will be based on improvement in participant's symptom score from baseline (pre-transplant) to intervention (post-transplant) 4 weeks, 12 weeks and 1 year following FMT. For participants with ARO colonization, determination of clearance of ARO based on stool culture for ARO at baseline, day 7, day 30 and 3 months following last FMT.

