### **Secondary Outcome Measurements for participants with IBD, MC or IBS:**

1. Evaluate efficacy and safety of FMT in patients with chronic gastronintestinal dysbiosis and antimicrobial resistant organism in the gut

2. Evaluate the Ulcerative Colitis Disease Activity Index from baseline and following each FMT using partial-MAYO score.
3. Evaluate Crohn's Diseases Activity Index (CDAI) change from baseline 4 weeks, 12 weeks and 1 year post-FMT.
4. Evaluate Microscopic colitis response to FMT using physician's global assessment and number of unformed bowel movements per 24 hours
5. Evaluate Irritable Bowel Syndrome Severity Scoring System (IBS-SSS) grade assessment change from baseline, 4 weeks, 12 weeks and 1 year post-FMT.

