### **Ulcerative Colitis**

The efficacy of FMT for UC will be determined based on changes to partial-MAYO score from baseline and at weeks 4, 12 and year 1, following the treatment. Partial-MAYO is a validated scoring system to determine the activity of UC. It uses the three non-invasive components of the full Mayo Score (stool frequency, rectal bleeding and Physician's global assessment) as perceived by the patient, to score ulcerative colitis patient's disease severity score. The index considers these three clinical parameters, each of which is assigned a score from 0 to 3 according to the clinical evaluation, with a total possible score of 9. Higher the score, more severe the disease; score of 0 to 1 is considered in remission; 2 – 4 mild; 5 – 7; moderate; > 7 severe colitis.

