### **Crohn's Disease**

CDAI is a validated instrument used in adults with active Crohn's disease. The index consists of eight factors, 2 of which are subjective: stool habits; pain; general well being; features of extra intestinal disease; use of opiates for diarrhea; abdominal mass; hematocrit (hct); and percentage of body weight below standard. Scores range from 0 to ~ 600: > 450 is severe disease; 220 – 450 moderately active disease; 150 – 219 mildly active disease. Clinical remission is defined as a CDAI score <150, clinical response is either a CDAI score <150 or a CDAI reduction of ≥100 from baseline.

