## **The Proposed Trial**

### **The proposed design of the study**

The design of this research is a prospective open-label trial using lyophilized or frozen FMT to evaluate efficacy of fecal microbiota transplantation for treatment of chronic gastrointestinal (GI) dysbiosis and clearance of antimicrobial resistant organism (ARO) from the GI tract of the ARO colonized individuals.

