### **The proposed type of statistical analyses**

The clinical response rate will be determined using standard binary outcome protocols. Also, logistic regression and survival analysis methods will be performed. The primary endpoints of clinical response, and treatment failure will be analyzed by logistical regression.

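### Dysbiosis group: the primary endpoint is stated in two unlinked forms with no lead visit, response is defined only for Crohn's disease, and no rule says how participants withdrawn for no improvement are counted

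*Combined protocol and SAP*

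**What the plan says.** **Primary outcome.** Primary Outcome Measurements bases efficacy in the dysbiosis group on improvement in "symptom score from baseline (pre-transplant) to intervention (post-transplant) 4 weeks, 12 weeks and 1 year following FMT". It names no instrument, no size of improvement and no lead visit. The same paragraph ties the visits of the antimicrobial-resistant-organism (ARO) group to the final dose ("day 30 and 3 months following last FMT"); the dysbiosis visits have no such anchor.

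**Primary endpoints in the analysis section.** The proposed type of statistical analyses states: "The primary endpoints of clinical response, and treatment failure will be analyzed by logistical regression".

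**Secondary outcomes.** The disease measures (partial Mayo, CDAI, IBS-SSS, and the two microscopic colitis measures) are listed as secondary. CDAI and IBS-SSS change have the same three visits as the primary outcome. For ulcerative colitis this list scores "from baseline and following each FMT using partial-MAYO score", whereas the Ulcerative Colitis section uses "changes to partial-MAYO score from baseline and at weeks 4, 12 and year 1, following the treatment".

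**Definitions.** For Crohn's disease, "clinical response is either a CDAI score <150 or a CDAI reduction of ≥100 from baseline". Ulcerative colitis has a remission band and severity bands, IBS has severity bands, and microscopic colitis has two measures without a threshold. Chronic severe constipation/dysbiosis is eligible under Participant inclusion criteria but has no measure.

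**Withdrawal.** GI Dysbiosis Participants gives FMT twice weekly for 4 weeks. Those without improvement at that point may continue for 4 more weeks or leave, by mutual decision. The same section says that those with no improvement after the 8th FMT are withdrawn to usual care.

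**Design and size.** The study is a "prospective open-label trial using lyophilized or frozen FMT", and no control arm is described. The 50 dysbiosis participants are justified by 5% response on placebo against 24% on FMT, 5% significance and 80% power.

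**The concern.** A change in score and a binary response are different endpoints. They can give different answers from the same data, and the plan calls each of them primary in a different place. With three unranked visits and no response threshold outside Crohn's disease, two analysts could follow the document faithfully and report different primary results. In an open-label study with no described control, pre-specification is one of the main protections against choosing the more favourable version after the data are seen.

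The withdrawal provision adds a second problem. Participants leave because they did not improve, so their 12-week and 1-year data would be missing because of the outcome itself. Whether they stay in the denominator affects the headline rate directly.

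**Working it through.** **1. Setting the sections side by side (dysbiosis group)**

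| Item | Primary Outcome Measurements | Statistical analyses section |
|---|---|---|
| Type | improvement in a score | binary response and binary failure |
| Visit | 4 weeks, 12 weeks, 1 year, none ranked | none stated |
| Threshold | none | none |

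| Condition | Measure that can be inferred | Response defined? | Failure defined? |
|---|---|---|---|
| Crohn's disease | CDAI | yes | no |
| Ulcerative colitis | partial Mayo | no (remission band only) | no |
| Microscopic colitis | global assessment, unformed stools per 24 hours | no | no |
| IBS | IBS-SSS | no (severity bands only) | no |
| Constipation/dysbiosis | none | no | no |

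**2. Time origin.** The first phase lasts 4 weeks and a second phase 4 more. Twelve weeks counted from the first dose and from the end of an 8-week course therefore differ by about 8 weeks. The text does not say which is meant.

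**3. Withdrawal point.** 2 per week × 4 weeks = 8 FMTs. The 8th FMT therefore falls at the same point as the 4-week decision, where one sentence allows continuation and the other withdraws the participant.

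**4. Reproducing the plan's 50.** Inputs from the sample size section: 5%, 24%, significance 5% (taken as two-sided), power 80%. With unpooled variance,

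n per arm = (1.960 + 0.842)² × (0.05 × 0.95 + 0.24 × 0.76) / (0.24 − 0.05)² = 7.849 × 0.2299 / 0.0361 = 49.98, so 50.

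With pooled variance the figure is 53. The stated 50 thus matches the size of *one arm* of a two-arm comparison of a binary response. That agrees with the statistical section rather than with a score change, and it says nothing about what 50 participants give in one arm.

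**5. Effect of the missing counting rule.** The plan gives no withdrawal count, so the number w is assumed. Take 12 responders, which is 24% of 50, and assume that every withdrawn participant is a non-responder. The rate among those remaining is 12/(50 − w), with exact (Clopper-Pearson) intervals:

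| Withdrawn and left out | Rate | 95% CI |
|---|---|---|
| 0 (all 50 counted) | 12/50 = 24.0% | 13.1% to 38.2% |
| 5 | 12/45 = 26.7% | 14.6% to 41.9% |
| 10 | 12/40 = 30.0% | 16.6% to 46.5% |
| 15 | 12/35 = 34.3% | 19.1% to 52.2% |
| 20 | 12/30 = 40.0% | 22.7% to 59.4% |

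The same 12 responders give anything from 24% to 40%.

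**6. Precision by condition.** With about a quarter of the group in one condition (12, assumed), 3/12 = 25% has an exact 95% CI of 5.5% to 57.2%.

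**The case against.** The strongest reply is that the two statements need not contradict each other. Improvement can be read as yes or no, as GI Dysbiosis Participants reads it, and the Crohn's Disease section turns a score change into a response. The statistical section could then simply be the binary form of the primary outcome. That reading is possible, so a reader who infers a proven contradiction goes too far. What stands is that no section makes the link, and that the statistical section adds treatment failure, which has no counterpart in the outcome section.

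A reader might also infer that no instrument is named at all, or that endpoint, visit and cut-off are all open. The documents do not support that. The disease sections let the measures be inferred for four conditions, the Crohn's cut-off and the ulcerative colitis remission band are fixed, and the visits are limited to three. The gaps that remain are the secondary label on those measures, the missing thresholds, and the absence of any measure for constipation/dysbiosis.

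Nor do the documents say that withdrawn participants will be excluded. They are silent, so the bias describes what an analysis of those remaining would show, not what the sponsor has planned. Finally, a regression without a comparator is not in itself an error in a one-arm study, and this point does not rest on it.

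**Conclusion.** The concern holds for the dysbiosis group and should be fixed before analysis. The ARO group has its own culture-based outcome and is not affected. As written, the primary result cannot be derived from the plan: two forms of endpoint are called primary without a link, no visit leads, response is defined for one of five eligible conditions, and failure is defined for none.

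The counting gap could move a 24% response rate to 30% or 40% with 10 or 20 withdrawals. Those counts are assumptions, and the illustration takes all withdrawn participants to be non-responders. The direction does not depend on the exact number: leaving out people removed for not improving raises the rate. No comparable figure is given for mean score change, because the plan specifies no analysis of it.

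The two withdrawal sentences conflict. This review takes no view on which should stand.

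**What to change.** 1. Align the primary outcome, secondary outcome and statistical sections on one primary endpoint at one pre-named visit with a stated time origin. Since the sample size and statistical sections are already binary, clinical response is the natural choice.
2. Define response before analysis for each eligible condition, including ulcerative colitis, microscopic colitis, IBS and constipation/dysbiosis. Reconcile the two timings for the partial Mayo score.
3. Report response as a proportion of all treated participants with an exact 95% CI, pooled and by condition. Count those withdrawn for no improvement as non-responders.
4. Make score change and the other visits secondary. Define treatment failure, or drop it as a primary endpoint.
5. State that 5% against 24% is a two-arm calculation (about 50 to 53 per arm), and describe what 50 in one arm gives as precision; for example, 12/50 gives 13.1% to 38.2%.
6. Reconcile the two withdrawal sentences in GI Dysbiosis Participants.

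**Cost.** This is mainly protocol and SAP wording, but agreeing response definitions for four conditions takes real work. The reported rate may be less favourable than one based on those remaining. Pooling mixes different conditions, and by-condition intervals will be wide, as the 3/12 example shows.

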### **The proposed frequency of analyses**

The analyses will be conducted following the data collection stage at the end study. An interim analysis will be performed after 15 patients have been recruited to assess safety and ongoing trial feasibility for the dysbiosis group.

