Microscopic colitis (MC) is a chronic inflammatory disease of the colon as manifested by chronic, watery, non-bloody diarrhea. MC usually occurs in middle-aged individuals with a female preponderance. Currently, there are limited treatment options for MC; budesonide may be effective for short-term treatment of MC and can improve quality of life. However, up to 80% will experience symptomatic relapse following cessation of budesonide. Routine maintenance treatment with budesonide is controversial as long-term treatment may increase the risk of steroid-related side effects.

IBS is characterized by chronic, relapsing abdominal discomfort and altered bowel movements – constipation, diarrhea or mixed (diarrhea and constipation). IBS affects approximately 15-20% of Canadians and its economic and social burden is estimated to be over \$6.5 billion per year in healthcare costs, work productivity losses, and reduced quality of life (QoL). The etiology and pathophysiology of IBS are not yet established, but appear to be a complex interplay between the host and environment factors. Currently, there are no evidence-based therapies available to cure IBS. Studies have shown that fecal microbiota transplantation (FMT) may be an effective IBS treatment. Given the lack of safe and effective treatment for IBD and IBS which are thought to be due to gastronintestinal dysbiosis, this study was conducted.

There is also some evidence in the literature showing efficacy of FMT in clearance of antimicrobial resistant organism (ARO) such as extended-spectrum of beta-lactamases (ESBLs), carbapenem resistant or vancomycin resistant enterococci from the gastronintestinal tract of colonized patients. There have been requests from clinicians to utlize FMT for eradication of ARO in rectally colonized patients admitted to an acute care facility in order to facilitate their discharge to a longterm care facility as they were otherwise eligible to be transferred.

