#### **ARO Participants**

Following informed consent and prior to receiving FMT, enrolled ARO participants will have their blood collected for Hepatitis BsAg, Hepatitis C Ab, HIV, Syphilis serologies. Blood is collected for these pathogens to determine their serostatus at the time of study enrollment. Participants are advised through the study consent that if their blood tests positive for any of these diseases, the researchers are required to notify the public health department and that the public health department may contact them.

At baseline, ARO participants will have medical history, physical exam done by the physician-researcher, and information on concomitant medications will be collected. The participants will receive a total of two lyophilized FMT (LYO-FMT) or frozen FMT enemas using stool samples collected from healthy, screened donor(s); the participant will receive the first FMT treatment week 1 and a second FMT will be administered within three weeks of first treatment. Participant's stool will be retested one week, one month and 3 months following the second FMT to determine whether the ARO has been eradicated.

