## GI Dysbiosis Participants

Following informed consent and pre-transplant, enrolled participants will have their blood collected for Hepatitis BsAg, Hepatitis C Ab, HIV, Syphilis serologies unless these serologies were performed within 3 months of enrollment. Blood is collected for these pathogens to determine their serostatus at the time of study enrollment and prior to receiving FMT.

All participants will be assessed at day 1 by the physician-investigator. A medical history and physical examination will be performed. In addition, optional blood and stool samples may be collected from IBD/IBS participants who consented for these samples prior to the FMT and at weeks 4, 12 and 6 months from FMT.

The participants will receive lyophilized FMT (LYO-FMT) or frozen FMT enemas using stool collected from healthy, screened donor(s). Participants will receive FMT treatment via retention enema(s) twice weekly for 4 weeks. If there is symptom improvement after 4 weeks of treatment, then the participants will receive FMT treatment once weekly for 4 additional weeks. If the participant does not experience symptom improvement after the initial 4 weeks of treatment, the physician-investigator will discuss options with the participant and a mutual decision will be reached to pursue an additional 4 weeks of FMT treatment or withdraw from the study and pursue usual care. When continued improvement is seen then the participants will receive FMT maintenance; the frequency of FMT treatment is participant dependent and is at the discretion of the physician-investigator and is based upon clinical exam and symptomatic improvement. If no improvement is seen after the 8th FMT, then the participant will be withdrawn from the study and s/he reverts to usual care for his/her condition. Participants can opt to receive maintenance FMT in the clinic or be trained by study staff for home administration.

At the time of each study visit and follow up, participants will be assessed for clinical response, including bowel movements and adverse reactions. Any participant who reports worsening symptoms or AE/SAE will return to the clinic for assessment by the physician investigator. At that time, the participant will undergo a physical exam. Additional tests may be ordered (i.e. blood work) at the discretion of the treating physician investigator.

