### **Adverse Event Reporting**

All adverse drug event (ADE) and serious adverse events (SAE) will be tracked in the participant's study file and REDCap and reported to Island Health's Clinical Research Ethics Board (CREB). As per Health Canada, a SAE is defined as "an adverse drug reaction that requires inpatient hospitalization or prolongation of existing hospitalization, that causes congenital malformation, that results in persistent or significant disability or incapacity, that is life threatening or that results in death". Each SAE that is attributed to FMT is subject to expedited reporting to Health Canada and should be reported individually in accordance with the data element(s) specified in the Health Canada/ICH Guidance Document E2A: "Clinical Safety Data Management: Definitions and Standards for Expedited Reporting". Expedited reports are required for events that meet all of these three criteria: serious, unexpected and a suspected causal relationship; this is defined as any untoward medical occurrence that at any dose results in

any one of the following: results in death; is life-threatening; requires inpatient hospitalization or prolongation of existing hospitalisation; results in persistent or significant disability/incapacity or is a congenital anomaly/birth defect. An event reaction causality scoring system will be used to determine the probability of the relationship of the event to study intervention. Source documents will be used to capture AEs and SAEs. All AEs will be reported to the CREB within 24 hours of the PI being aware of the event.

Known side effects of FMT are described in table 6.0; these potential effects are listed in the informed consent and participants are advised to report these and any other effects that they feel is relevant or causing concern.

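### Safety of FMT in ARO participants is a stated outcome, but no adverse-reaction assessment is scheduled for them and the interim safety analysis is worded for the dysbiosis group

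*Combined protocol and SAP*

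**What the plan says.** **The outcome.** Item 1 of the secondary outcomes is to "Evaluate efficacy and safety of FMT in patients with chronic gastronintestinal dysbiosis and antimicrobial resistant organism in the gut". The heading over the list reads "Secondary Outcome Measurements for participants with IBD, MC or IBS", so the item names the ARO cohort and the heading omits it.

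**The two schedules.** Each cohort has its own section.

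- GI Dysbiosis Participants: "At the time of each study visit and follow up, participants will be assessed for clinical response, including bowel movements and adverse reactions". The same section says that a participant with worsening symptoms or an adverse event returns to the clinic for assessment.
- ARO Participants: a baseline history, physical examination and medication record, then two FMT enemas. After that, "Participant's stool will be retested one week, one month and 3 months following the second FMT to determine whether the ARO has been eradicated". No clinical or adverse-reaction assessment after baseline is stated.

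**The interim analysis.** The proposed frequency of analyses states: "An interim analysis will be performed after 15 patients have been recruited to assess safety and ongoing trial feasibility for the dysbiosis group".

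**Provisions not limited to one cohort.** Under Adverse Event Reporting, "All adverse drug event (ADE) and serious adverse events (SAE) will be tracked in the participant's study file and REDCap". That section also names source documents as a means of capture and says participants are advised to report effects. The DMC normally meets after the first 20% of participants and when enrollment ends, and it receives each serious adverse event judged at least possibly related. The Enrollment stopping rules count any FMT recipient.

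**The concern.** A stated outcome needs a stated way of collecting it. For the ARO cohort the plan says how events are filed and reported once known, but not when anyone asks about them. Followed as written, harms would be solicited in one cohort and left to chance in the other.

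The effects at risk of being missed are the minor ones. The FMT Side Effects table lists hard stool, flatulence, stomach discomfort, increased appetite, nausea and rectal discomfort. None of these would ordinarily be serious, so none would usually reach the DMC. The background says clinicians asked for this use in "rectally colonized patients admitted to an acute care facility in order to facilitate their discharge". In patients of that kind, a minor bowel complaint that nobody asks about is easily lost among other symptoms.

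The 20 ARO participants are a pilot meant to inform whether further study is feasible. If non-serious harms are under-counted, the safety description carried forward from the pilot would look more favourable than it should.

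**Working it through.** The point turns on coverage, and no figure in the plan is in dispute. The first step compares the texts; the rest gives scale.

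**1. Coverage by cohort**

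| Provision | Dysbiosis | ARO | Acts on |
|---|---|---|---|
| Safety as an outcome | Yes | Yes, in the item but not the heading | – |
| Adverse-reaction assessment at visits | Yes | Not stated | Finds events |
| Interim safety analysis | Yes | Unclear | Recorded events |
| Tracking and source documents | Yes | Yes | Events elicited, volunteered or noted |
| DMC meetings | Yes | Yes | Mainly serious events |
| Stopping rules | Yes | Yes | Serious events only |

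Only the second row is a scheduled means of finding events, and it is the row missing for ARO participants.

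**2. Size of the cohort**

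Recruitment plans 50 dysbiosis and 20 ARO participants. 20 / (50 + 20) = 20/70 = 28.6%.

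**3. What 20 participants can show with complete capture**

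- Zero events, one-sided 95% upper limit: 1 − 0.05^(1/20) = 0.139, or 13.9%.
- Chance of recording at least one event at a per-participant rate p: 1 − (1 − p)^20. This is 18% at p = 1%, 64% at p = 5% and 88% at p = 10%.

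**4. Effect of incomplete capture (assumed values)**

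The documents give no capture rate, so a range is shown. If each affected participant is recorded with probability c, the recorded rate is c × p. Take p = 10%, the figure the side-effect table gives for hard stool.

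- c = 1: recorded rate 10%, chance of at least one record 88%.
- c = 0.5: recorded rate 5%, chance 64%.
- c = 0.1: recorded rate 1%, chance 18%.

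With zero recorded events and c = 0.5, the upper limit on the true rate becomes 13.9% / 0.5 = 27.8%.

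These figures illustrate direction and scale and are not predictions. The table does not say which population or how many FMTs its frequencies come from. The 13.9% limit reflects the sample size and is not itself evidence of poor capture.

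**5. Timing of the DMC review**

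20% of 70 = 14 participants, if counted across the whole trial. That is close to the 15-patient interim and is not restricted by cohort. No minimum number of ARO participants is set, so the first review could include few or none.

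**The case against.** The strongest reply is that the trial-wide safety provisions already reach the ARO cohort. Much of this stands, and it rules out several stronger readings that a reader might infer.

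- **That ARO harms reach the trial only through self-report.** The documents do not support this. Source documents are a named route of capture, and for an inpatient they could include notes made by others. However, a source document holds only what someone elicited, observed or was told, and the ARO section creates no clinical record after baseline.
- **That nobody reviews ARO safety in aggregate before the end.** This is not supported either. The DMC meetings and stopping rules cover all FMT recipients, although they concern mainly serious events.
- **That the interim safety analysis definitely excludes ARO participants.** The closing phrase on the dysbiosis group may attach to feasibility alone. That is plausible, since the ARO cohort is itself the feasibility pilot. The ambiguity still needs resolving.
- **That some ARO participants could not report for themselves.** Study Population allows consent by a representative, but the Participant inclusion criteria require ability to consent. That is a separate inconsistency and does not show that such patients will be enrolled. The background reports clinicians' requests and does not define the ARO population.
- **That a planned comparison or decision rule would be biased.** No between-cohort safety comparison is planned, and no harm-rate criterion for feasibility is given.

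It can also be said that the ARO cohort's primary outcome is clearance. That is true, but safety in these participants is still listed as an outcome.

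**Conclusion.** The concern holds in a limited form. Safety in ARO participants is a named outcome with no scheduled assessment of adverse reactions, and it is unclear whether the interim safety analysis includes them. Serious events have a route to oversight once recorded. Non-serious events depend on unsolicited reports and source documents.

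This affects 20 of 70 planned participants (28.6%). Under-counting is likely, but its amount cannot be derived from the documents. The conclusion assumes that the ARO section is read as that cohort's full schedule and that staff do not ask about events beyond what is written. If staff already do so, the defect is one of documentation and the same wording change resolves it.

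**What to change.** 1. Apply the sentence on assessing adverse reactions, now under GI Dysbiosis Participants, to all participants.
2. State under ARO Participants that adverse events are solicited at the second FMT and at the 1-week, 1-month and 3-month stool-retest time points. The protocol does not say the retests are in-person visits, so allow a phone call where they are not.
3. State under The proposed frequency of analyses that the interim safety analysis includes all ARO participants treated to date, tabulated separately.
4. Correct the secondary-outcome heading so that it matches item 1.
5. The sponsor should reconcile whether the return-to-clinic sentence in the dysbiosis section applies to ARO participants. No clinical rule is proposed here.

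The cost is protocol wording, a short adverse-event form, possibly some phone calls and slightly more data entry. No additional patients are needed and neither sample size changes.
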